2. GENERAL ANALYSIS CONSIDERATION

Time to event or duration of event endpoints will be based on the actual event date (or censoring date) rather than visit number or visit label. Missing efficacy or safety data will not be imputed unless otherwise specified.

In general, the baseline value is defined as the last valid measurement on or prior to the first dose of study treatment. For by-visit analysis, visit windows will be used to associate assessment with a scheduled visit and will be created in reference to the date of first dose of study treatment to assign visit number based on assessment date.

2.1. Analysis Sets

Response-evaluable Population

The Response-evaluable Population is defined as all enrolled subjects who received at least one dose of study treatment (ibrutinib or MEDI4736) and provided at least one post-baseline response assessment. This population includes all the qualified subjects from both Phase 1b and Phase 2. The Response-evaluable Population will be used as the primary population for analyses based on overall response rate. In the analysis, subjects who had clinical progression per investigator will be included in the response-evaluable population.

Safety Population (Treated Population)

Safety population (Treated Population) includes all subjects who were enrolled in the study and received at least 1 dose of study treatment (ibrutinib or MEDI4736). The safety population will

be used to summarize the safety (including dosing) data and for the analysis of PFS, OS and ORR sensitivity analysis.

DLT Evaluable Population for Phase 1b

DLT evaluable population includes Phase 1b subjects who received study treatment and did not meet the criteria for subject replacement during the DLT observation period.

2.2. Definition of Subgroups

For the DLBCL cohort, a subgroup analysis will also be conducted to calculate ORR and its 95% CI for

- GCB and non-GCB DLBCL types per IHC test.
- GCB, ABC and Unclassified DLBCL types per GEP test.

3. SUBJECT INFORMATION

3.1. Subject Disposition

Subject disposition will be summarized by each tumor type cohort. Subject enrollment will be summarized by region, country, and investigator.

Time on study is defined in the same way as overall survival with reversed censoring, i.e., subjects who died will be censored at death date. The Kaplan-Meier method will be used to estimate the median time on study.

3.2. Demographics and Baseline Characteristics

Baseline characteristics and demographic information at baseline will be summarized with descriptive statistics by tumor type cohort.

3.3. Prior and Concomitant Medications

Medications will be coded to a generic name and an Anatomical Therapeutic Chemical (ATC) class per the World Health Organization (WHO) drug dictionary. Concomitant medications will be summarized by therapeutic class and preferred term and by tumor type cohort. Concomitant medications are defined as medications that were taken at any time on treatment (i.e. from the date of the first dose of study treatment through the date of the last dose of study treatment). The following concomitant medications will be summarized separately: growth factors, blood supportive products and immunoglobulin, CYP3A inhibitors/inducers, anticoagulants and/or antiplatelets.

3.4. Extent of Exposure to Study Treatment

Exposure to study treatment will be summarized by tumor type cohort. Descriptive statistics will be provided for treatment duration and dosing information (e.g. total cumulative dose administered, relative dose intensity, dose reduction due to adverse events) for all study treatments.

3.5. Previous Treatment History and Subsequent Antineoplastic Therapies

Previous treatment history and subsequent antineoplastic agents will be summarized separately.

4. EFFICACY AND SAFETY ANALYSES

4.1. Efficacy Analyses

Efficacy endpoints and analysis methods are summarized in Table 1.

Table 1: Summary of Efficacy Analyses

Endpoint	Definition	Analysis Method
Primary Endpoint		
Overall Response Rate (ORR)	Proportion of subjects achieving the best overall responses of complete response (CR) or partial response (PR) with confirmation per the investigator using the Revised Criteria for Response Assessment of Malignant Lymphoma (Cheson 2014)	
Primary (Response-evaluable population)
 
 Proportion and 2-sided 95% CI based on exact Binomial distribution (Clopper-Pearson) 
Sensitivity (Treated population)
 
 Proportion and 2-sided 95% CI based on exact Binomial distribution (Clopper-Pearson) Waterfall plot of best change from baseline of tumor load from target lesion(s) 
Subgroup (Response-evaluable and treated population): For the DLBCL cohort, a subgroup analysis will also be conducted to calculate ORR and its 95% CI for
 
 GCB and non-GCB DLBCL types per IHC test GCB, ABC and Unclassified DLBCL types per GEP test
Secondary Endpoints		
Duration of Response (DOR)	Duration of time from the date of initial response to the date of disease progression or the date of death due to any cause, whichever occurs first	
Primary (Response-evaluable population)
 
 Kaplan-Meier estimate
Progression Free Survival (PFS)	Duration of time from the first dose date of study treatment (ibrutinib or MEDI4736) to the first documentation of disease progression or death	
Primary (Treated population)
 
 All PD and death considered as events regardless of any anticancer therapy prior to PD Kaplan-Meier curve

Endpoint	Definition	Analysis Method
	from any cause, whichever occurs first.	
Overall Survival (OS)	Duration of time from the first dose date of study treatment (ibrutinib or MEDI4736) to the date of death due to any cause	Primary (Treated population) 
 All death considered as events regardless any anticancer therapy prior to death Kaplan-Meier curve

4.2. Safety Analyses

Safety data will be summarized by tumor type cohorts. Table 2 summarizes the safety analyses to be performed for all tumor type cohorts.

Adverse events (AEs) will be coded in accordance with the Medical Dictionary for Regulatory Activities (MedDRA). Severity of AEs will be graded by the investigator according the NCI-CTCAE v4.03.

All laboratory values will be converted to and reported as international standard (SI) units. In general, only data from the central laboratory will be summarized and analyzed. Laboratory parameters will be graded using the NCI CTCAE v4.03.

Unless otherwise specified, only baseline and post-baseline values collected during the treatment-emergent period will be included in the safety analysis. A treatment-emergent adverse event is defined as any event that begins or worsens in either intensity or frequency on or after the first dose of study treatment (either ibrutinib or MEDI4736). Only treatment-emergent adverse events (TEAEs) occurring and reported during the study period will be included in the adverse event summaries. The TEAEs will be derived as those events that 1) occur after the first dose of study drug (either ibrutinib or MEDI4736), through the 30 days following the last dose of ibrutinib or 90 days following the last dose of MEDI4736 (whichever date is later); 2) any event with missing onset date and its resolution date during the treatment phase; 3) any event that is considered study drug-related regardless of the start date of the event; or 4) any event that is present at baseline but worsens in severity, seriousness, or becomes subsequently considered drug-related by the investigator.

Table 2: Summary of Safety Analyses

Safety Assessment	Definition	Analysis Methods
Safety and tolerability	
AE: TEAEs, SAEs, grade 3 or worse TEAEs, related TEAEs, TEAEs leading to treatment discontinuation, TEAEs leading to dose reduction, TEAEs leading to death, protocol- defined events of special interest, and other safety observations
 
Worst post-baseline toxicity grade for selected lab tests: Worst post-baseline toxicity grade, Hgb, creatinine clearance, abnormal uric acid, liver function abnormalities
 
Vital signs (blood pressure, heart rate, temperature, respiratory rate), and weight
	Descriptive summary statistics and/or listings

AE: adverse event; SAE: serious adverse event; TEAE: treatment-emergent adverse event

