	A primary objective is to evaluate safety and tolerability of ibrutinib in combination with MEDI4736. AEs including DLTs, laboratory values, and dosing data will be listed and summarized by tumor type and dose cohort. Secondary objectives are to evaluate efficacy and PK and pharmacodynamics in subjects receiving the combination regimen. ORR and DOR will be calculated and summarized by tumor type and dose cohort descriptively. PK and pharmacodynamics (ie, BTK) data will be evaluated by tumor type and dose cohort.			
	Phase 2: Phase 2 will use the RP2D ascertained in Phase 1b to treat approximately 73 subjects (39 FL and 34 DLBCL subjects). For Phase 2 the following analyses will be undertaken:			
	Primary Efficacy Endpoint:			

	The primary efficacy endpoint is the ORR in each of the two cohorts. The observed ORR along with its 95% confidence interval will be calculated for each tumor tume.		
	for each tumor type.		
	Secondary Efficacy Endpoints:		
	• DOR will be calculated and summarized by descriptive statistics for responders by tumor type. The Kaplan-Meier estimate will be provided for DOR if a sufficient number of responders are observed.		
	• PFS and OS will be evaluated by tumor type with Kaplan-Meier estimates.		
	• PK and pharmacodynamics profiles will also be evaluated by tumor type.		
	Exploratory Efficacy Analysis:		
	The exploratory efficacy variables will be summarized descriptively and include the following:		
	Immune cell subsets		
	• Non-BTK related pharmacodynamics (ie, ITK)		
	• Chemokine/cytokine levels		
	• Genes and proteins associated with sensitivity or resistance to ibrutinio and/or MEDI4736 (ie, PD-L1)		
	Rate and duration of MRD negativity		
	For each cohort, a subgroup analysis will be conducted to calculate ORR and its 95% confidence interval based on PD-1 ligand expression (positive versus negative). For the DLBCL cohort, a subgroup analysis will also be conducted based on subjects with GCB and non-GCB subtype, respectively.		
	Safety Analysis:		
	AEs, SAEs, laboratory data, vital signs, other relevant safety data, and dosing data will be listed and summarized by cohort.		
Sample Size	Phase 1b:		
Determination:	6-36 subjects for DLT assessment (6-9 subjects in up to 4 dose de- escalation cohorts, regardless of tumor type)		
	Phase 2:		
	Approximately 73 response-evaluable subjects (including those subjects treated at the RP2D in Phase 1b but with tumor type as defined for Phase 2).		
	For FL:		

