10.6.1 Phase 1b Analyses

The primary objective of Phase 1b is to determine the RP2D and to evaluate safety and tolerability of ibrutinib in combination with MEDI4736. An algorithm-based 6+3 dose de-escalation design is used to find the RP2D of the combination regimen and to characterize the most frequent adverse events and DLTs. DLTs will be evaluated and will include all adverse events experienced through Phase 1b. Study-drug exposure and laboratory data will be evaluated and summarized by dose cohort.

The secondary objectives are to evaluate efficacy, PK, and pharmacodynamics in subjects receiving ibrutinib in combination with MEDI4736. The observed ORR along with the corresponding 95% confidence interval based on exact binomial distribution and duration of response (DOR) will be calculated and summarized with descriptive statistics by dose cohort and tumor type. PK and pharmacodynamics (ie, BTK) data will be summarized by dose cohort and tumor type.

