1.5. Planned Analyses

1.5.1. Phase 1b Analyses

A Dose Level Review Committee will be established to evaluate the safety data from each cohort of the Phase 1b on an ongoing basis. Dose de-escalation will follow the 6+3 design described in Section 3.1.1 and up to 4 cohorts including 3 dose de-escalation cohorts (1, -1A, -1B, and -2) will be enrolled if needed to determine the RP2D for the combination therapy.

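### The SAP drops the protocol's by-dose Phase 1b summaries without listing the change, and its analysis sets omit the RP2D limit it places on Phase 2

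*SAP*

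**What the plan says.** For Phase 1b, the statistical methods in the Protocol Synopsis say that "AEs including DLTs, laboratory values, and dosing data will be listed and summarized by tumor type and dose cohort". Protocol 10.6.1 adds that "Study-drug exposure and laboratory data will be evaluated and summarized by dose cohort", and asks for Phase 1b ORR and DOR by dose cohort and tumour type.

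The SAP groups differently. Section 4.2 says "Safety data will be summarized by tumor type cohorts" and Section 3.4 says "Exposure to study treatment will be summarized by tumor type cohort". Table 1 (Section 4.1) covers ORR and DOR with no dose grouping, although SAP 1.2 keeps both as Phase 1b secondary endpoints. SAP 1.5.1 still provides for "up to 4 cohorts including 3 dose de-escalation cohorts".

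On analysis sets, SAP 2.1 says of the Response-evaluable Population: "This population includes all the qualified subjects from both Phase 1b and Phase 2". It does not define what qualifies a subject. It also says "Safety population (Treated Population) includes all subjects who were enrolled in the study and received at least 1 dose of study treatment", and uses that set for safety, PFS, OS and the sensitivity analysis of ORR. Neither definition mentions the RP2D. Elsewhere the SAP does: the Phase 2 note in 1.1, the objective in 1.3 and the sample sizes in 1.4 all tie Phase 2 to the RP2D.

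**The concern.** Safety and tolerability of the combination is a Phase 1b primary endpoint, and the protocol commits to reporting it by dose cohort. If the trial de-escalates, a table split only by tumour type cannot show how the dose levels differ. A reader also cannot recover the profile of the dose taken into Phase 2.

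The efficacy sets carry a related risk. Protocol 3.1.1 keeps Phase 1b subjects who were not treated at the RP2D on their assigned dose and follows them for response and survival, so they will have data. A programmer working from SAP 2.1 and Table 1 alone would find no instruction to leave them out of Phase 2 ORR, DOR, PFS or OS.

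SAP Section 5 records departures as small as a change of terminology, so a reader would take its silence to mean that the by-dose summaries are still planned.

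**Working it through.** **1. The plan's own design figures.** For a two-stage rule that stops at r1 or fewer of n1 and rejects at R or more of n, P(reject) = Σ over x > r1 of b(x; n1, p) × P(Y ≥ R − x), with Y ~ Bin(n − n1, p). Inputs are from SAP 1.4, with the futility stop treated as binding.
- FL (6/19, then 17/39): 0.0455 at a true ORR of 30%, 0.804 at 50%.
- DLBCL (1/9, then 9/34): 0.0474 at 15%, 0.811 at 35%.

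These agree with the stated one-sided 0.05, read as a ceiling, and 80% power. They assume 39 and 34 subjects at the RP2D.

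**2. Phase 1b summaries side by side.**

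| Item | Protocol | SAP |
|---|---|---|
| AEs, DLTs | tumour type and dose cohort (Synopsis) | AEs by tumour type (4.2); no DLT entry in Table 2 |
| Laboratory | dose cohort (10.6.1; Synopsis adds tumour type) | tumour type (4.2) |
| Exposure | dose cohort (10.6.1; Synopsis adds tumour type) | tumour type (3.4) |
| ORR, DOR | dose cohort and tumour type (10.6.1) | no dose grouping (Table 1) |

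SAP 2.1 says that the "DLT evaluable population includes Phase 1b subjects who received study treatment and did not meet the criteria for subject replacement" in the observation period, but neither Table 1 nor Table 2 uses that population. SAP 1.1 sends the reader to a Section 4.2 on study treatment for the cohort definitions. SAP 4.2 is the safety section, so the SAP never gives the doses of the de-escalation cohorts. Section 5 lists the interim timing for each tumour type, the enrolment hold and a terminology change, and none of the differences in the table.

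**3. How many subjects could be off the RP2D.** SAP 1.4 allows 6 to 9 subjects in each of up to four dose cohorts.
- RP2D is Cohort 1: none.
- RP2D is -1A or -1B: up to 9 in Cohort 1 plus up to 9 in the parallel cohort, so up to 18.
- RP2D is -2: three other cohorts of 6 to 9, so 18 to 27.

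With k such subjects added to the 73 of Phase 2, the share is k/(73 + k):
- 9/82 = 11%
- 18/91 = 20%
- 27/100 = 27%

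**4. What pooling can hide.** As an illustration, 3 of 6 subjects with a DLT at one level and 1 of 6 at the RP2D pool to 4/12 = 33%, which hides 50% against 17%.

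**5. Efficacy, only on a literal reading of SAP 2.1.** Assume 9 off-RP2D subjects, all of one tumour type, with the RP2D at the alternative rate and the others at the null rate.
- FL: 9/48 = 19% of the set; pooled ORR (39 × 0.50 + 9 × 0.30)/48 = 46%, against 50% at the RP2D.
- DLBCL: 9/43 = 21% of the set; pooled ORR (34 × 0.35 + 9 × 0.15)/43 = 31%, against 35%.

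**The case against.** **The SAP already restricts Phase 2 to the RP2D.** Sections 1.1, 1.3 and 1.4 say so, and the undefined word in 2.1 can be read in their light. This stands. A reader might infer that the SAP plans to pool efficacy across doses, but that requires reading 2.1 and Table 1 in isolation. The efficacy defect is an inconsistency within the SAP. It is still worth correcting because it sits in the definitions from which datasets are built.

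**The all-dosed Treated set comes from the protocol.** Protocol 10.1.1 and 10.1.2 define it that way, and 10.6.2.2 uses the Safety Population for PFS and OS. So it is not a SAP departure, but the gap between that set and the Phase 2 target remains.

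**Phase 1b is still answered.** A reader might infer that the objective of finding the RP2D fails. It does not: the 6+3 rule in SAP 1.1 and the cohort-by-cohort committee review in SAP 1.5.1 determine the dose without the pooled tables. Nor does either document define the primary endpoint as safety at each dose. The by-dose split is a commitment about summaries.

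**De-escalation may never have happened.** Phase 2 enrolment starts only once the RP2D is set, and SAP Section 5 describes discontinuations already seen, so the authors probably knew the dose. The documents do not report it. Under the 6+3 rule, the chance that Cohort 1 becomes the RP2D is P(≤1 of 6) + P(2 of 6) × P(0 of 3), which is 0.96, 0.78 or 0.53 at assumed DLT rates of 10%, 20% or 30%. The 27-subject case needs three cohorts each with exactly 2 of 6 and then at least 1 of 3. For one cohort that probability peaks at 0.244 (DLT rate about 0.39), so for three independent cohorts it is at most 0.244³ = 1.5%. This limits the size of the point but does not excuse dropping a protocol analysis without listing it.

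**Conclusion.** The point holds as two linked defects. First, SAP 3.4, 4.1 and 4.2 leave out the by-dose Phase 1b summaries that the protocol requires, and Section 5 does not list the departure. Second, SAP 2.1 and Table 1 omit the RP2D limit that SAP 1.1, 1.3 and 1.4 place on Phase 2.

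The effect of pooling depends on de-escalation, which the documents neither report nor exclude. If it occurs, off-RP2D subjects would be about 11% to 20% of the safety set in the more ordinary cases and 27% in the extreme one. These shares assume cohorts without replaced subjects and a Phase 2 safety set of exactly 73. If Cohort 1 is the RP2D, nothing is pooled across doses, but the missing DLT summary remains.

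It would be wrong to describe the other dose levels as ones that failed. If -1A or -1B is chosen, the parallel cohort need not have met the de-escalation criterion. The accurate term is non-RP2D dose levels. The change should be made because a stated SAP rule conflicts with the protocol on how a primary endpoint is reported, and because the correction is cheap.

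**What to change.** 1. In SAP 3.4, 4.1 and 4.2, summarise Phase 1b AEs, DLTs (on the DLT Evaluable Population), laboratory and exposure data, and Phase 1b ORR and DOR, by dose cohort and tumour type as the protocol requires. State the cohort definitions in the SAP or correct the cross-reference in 1.1.
2. Keep the Safety population unrestricted for safety. SAP 2.1 makes Safety and Treated one set, and Phase 1b response needs subjects at every dose, so adding an RP2D limit to the existing definitions would remove subjects who are needed elsewhere. Instead, add to SAP 2.1 and Table 1 separate Phase 2 efficacy sets, one response-evaluable and one treated. Limit both to subjects treated at the RP2D with the Phase 2 tumour type, and use them for Phase 2 ORR, DOR, PFS and OS.
3. If the by-dose summaries are dropped deliberately, say so and why in Section 5. If no de-escalation took place, one sentence recording that would settle the pooling question.

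The cost is SAP wording, one added table grouping and the extra set definitions. The Phase 2 sizes stay at 39 and 34, and the alpha and power reproduced above are unchanged.

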7.1.2 Laboratory

Local laboratories will be used except for certain biomarker assays and in cases where a specialized laboratory is needed.

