7.1.2.1. Hematology

Hematology parameters will include a complete blood count: white blood cells, red blood cells, hemoglobin, hematocrit, platelets, neutrophils, lymphocytes, monocytes, eosinophils, basophils and bands (if reported). These should be performed at the site's local laboratory.

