7.1.2.2. Chemistry (Serum)

Serum chemistry parameters will include sodium, potassium, chloride, blood urea nitrogen (BUN), creatinine, glucose, calcium, total protein, albumin, AST, ALT, alkaline phosphatase, total bilirubin, lactate dehydrogenase (LDH), phosphate, uric acid, magnesium and bicarbonate. These should be performed at the site's local laboratory.

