1. INTRODUCTION

This statistical analysis plan (SAP) lays out key elements including definitions and statistical methods for analysis of data in evaluation of efficacy and safety for the PCYC-1136-CA study. Analyses of pharmacokinetics data and biomarkers will be addressed in separate documents.

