1.2. Endpoints

Primary Endpoints

Phase 1b:

- Recommended Phase 2 Dose (RP2D) of ibrutinib in combination with MEDI4736
- Safety and tolerability of ibrutinib in combination with MEDI4736

Phase 2:

- Overall Response Rate (ORR)

Secondary Endpoints

Phase 1b:

- Overall response rate (ORR)
- Duration of response (DOR)

Phase 2:

- DOR
- Progression-free survival (PFS)
- Overall survival (OS)

Safety Assessments

Safety and tolerability assessments include adverse events, clinical laboratory tests, and vital signs.

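### The SAP restricts laboratory summaries to central-laboratory data, but under the protocol every laboratory test it names is done locally and no central safety laboratory exists

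*SAP*

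**What the plan says.** SAP Section 4.2 gives one rule on the source of laboratory data: "In general, only data from the central laboratory will be summarized and analyzed". It states no exception. Table 2 in the same section lists the laboratory content of the safety analysis: "Worst post-baseline toxicity grade, Hgb, creatinine clearance, abnormal uric acid, liver function abnormalities". SAP Section 1.2 makes laboratory tests one of three safety assessments ("Safety and tolerability assessments include adverse events, clinical laboratory tests, and vital signs") and lists "Safety and tolerability of ibrutinib in combination with MEDI4736" as a Phase 1b primary endpoint.

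Protocol Section 7.1.2 opens with the rule for where tests are run: "Local laboratories will be used except for certain biomarker assays and in cases where a specialized laboratory is needed". Section 7.1.2.1 says of the hematology panel: "These should be performed at the site's local laboratory". The chemistry panel in Section 7.1.2.2 ends: "total bilirubin, lactate dehydrogenase (LDH), phosphate, uric acid, magnesium and bicarbonate. These should be performed at the site's local laboratory". Section 7.1.2.5 ties creatinine clearance to the local laboratory as well. Section 10.7.2, which plans the laboratory analysis, says that local results are converted using the normal ranges and put into SI units. It then calls for descriptive statistics, percent change from baseline and shifts to the worst grade.

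**The concern.** The two documents name opposite sources for the same tables. A programmer who follows the SAP literally has no protocol-scheduled hematology or chemistry results to put into the worst-grade summaries. A programmer who uses the local data departs from the SAP with no recorded reason.

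Adverse event tables do not fully replace the laboratory summaries. Under Protocol Section 7.1.1.5 an abnormal result becomes an adverse event only if it meets one of the listed conditions, such as symptoms, further treatment or tests, active management, or the investigator's judgment that it is clinically significant. A graded abnormality that meets none of them appears only in the laboratory outputs. The protocol itself flags cytopenias with ibrutinib (Section 1.3.4.3) and raised transaminases with antibodies against PD-1 or PD-L1 (Section 11.4.6.4), so these are summaries a reader of the report will want.

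**Working it through.** No arithmetic beyond counting applies. The check maps each laboratory item in SAP Table 2 to the protocol section that assigns its laboratory.

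| SAP Table 2 item | Protocol section | Laboratory assigned |
|---|---|---|
| Hemoglobin | 7.1.2.1 Hematology | Local |
| Uric acid | 7.1.2.2 Chemistry | Local |
| Liver function (AST, ALT, alkaline phosphatase, bilirubin) | 7.1.2.2 Chemistry | Local |
| Creatinine clearance | 7.1.2.5 | In conjunction with the local laboratory |

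Result: 4 of 4 items are local and 0 of 4 are central. Appendix 1 schedules creatinine clearance only at Screening, so a post-baseline value calculated by Cockcroft-Gault would use serum creatinine from the chemistry panel, which is also local. Table 2 refers to selected tests without closing the list, but any other hematology or chemistry test chosen would be local for the same reason.

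Next, is there a central laboratory elsewhere in the protocol that the SAP could mean?

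- All 8 laboratory subsections of Protocol Section 7.1.2 (7.1.2.1 to 7.1.2.8) name a local laboratory, and none names a central one. For pregnancy, this is stated for the serum test at Screening.
- The two exceptions at the head of Section 7.1.2 do not help. Biomarker assays fall outside this SAP ("Analyses of pharmacokinetics data and biomarkers will be addressed in separate documents"). The specialized laboratory is not called central and is not assigned any Table 2 test.
- Protocol Section 10.7.2 refers to local results and to no other source.

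Last, did the SAP change the source on purpose? Section 5 lists four changes from the protocol: interim timing for FL, interim timing for DLBCL, the hold on enrolment during the interim analysis, and a switch of terminology from safety endpoints to safety assessments. A change of laboratory source is not among them.

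Reach: SAP Section 1.2 lists adverse events, laboratory tests and vital signs. The sentence touches one of these three.

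**The case against.** The best case on the other side accepts the mismatch and disputes its weight.

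- **It would be noticed.** If no central data exist, the tables come out empty at the first run, so nothing is silently biased. The sentence may be leftover template text. Both points are plausible, but neither makes the sentence correct, and the documents do not show how it arose.
- **The qualifier.** The rule holds only *in general*, which leaves room for exceptions. Here the exception would have to cover every laboratory item named in Table 2, and a rule with no remaining cases cannot be what was meant.
- **Listings survive.** Table 2 allows listings as well as summary statistics, and the rule limits only what is summarized and analyzed. This is true and narrows the loss to the summaries.
- **Adverse event capture.** Many important laboratory abnormalities reach the adverse event tables through Protocol Section 7.1.1.5. This also stands. What remains exposed is the set of graded abnormalities that meet none of that section's conditions.
- **No decision depends on it.** The recommended Phase 2 dose rests on DLT counts, DLTs are adverse events, and Protocol Section 10.7 plans no formal testing of safety data. This is correct, and it limits the finding to reporting.
- **The wider count adds little.** Protocol Section 10.7.2 summarizes only hematology and chemistry, so the 4 of 4 count carries the argument. The 8 of 8 count serves only to show that no central laboratory is described elsewhere in Section 7.1.2.
- **Silence in SAP Section 5 is weak evidence.** That section speaks of a major change and may not be exhaustive, and the Laboratory Manual is not available here. A central laboratory could therefore have been added without trace in these documents. The section does record an item as small as a change of terminology, so a deliberate change of data source would be expected there.

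**Conclusion.** The concern holds. The SAP states a rule that contradicts Protocol Sections 7.1.2 and 10.7.2. Applied literally, it removes all protocol-scheduled hematology and chemistry results from the Table 2 laboratory summaries: 4 of 4 named items are local and 0 are central.

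The effect is on reporting only. Local data are still collected, and the outputs for adverse events, serious adverse events, events of special interest, DLTs and efficacy do not depend on this sentence. It should still be corrected, because laboratory tests are one of the three stated safety assessments and safety and tolerability is a Phase 1b primary endpoint.

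The conclusion assumes that no central safety laboratory was introduced outside these documents. If one was, the fault becomes an undocumented change of data source.

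**What to change.** Replace the sentence in SAP Section 4.2 with wording such as: *Local laboratory results, standardized with the local normal ranges and SI units as set out in Protocol Section 10.7.2, will be summarized and analyzed.*

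If a central safety laboratory was in fact introduced, describe it in the protocol, enter the change in SAP Section 5, and state how local results will be used alongside central ones.

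The first route costs one sentence and uses data already collected, with the method the protocol already gives. The second costs one entry in SAP Section 5 and a protocol clarification.
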